4.1.3 TAVI and Silent Cerebral Ischemia

In addition to clinical stroke, there is increasing recognition of the importance of subclinical manifestations of periprocedural cerebral embolization in cardiac procedures in general and TAVI in particular.²⁸⁻³⁰ A growing body of evidence indicates that clinically silent cerebral ischemia is common after TAVI and may have an important impact on clinical and neurocognitive outcomes.

Diffusion-weighted magnetic resonance imaging (DW-MRI) is a highly sensitive and specific technique to visualize acute ischemia.³¹ Acute ischemia presents on DW-MRI as a hyperintense area against the dark background of normal tissue, allowing detection of even small lesions. MRI-based methods have greater sensitivity to detect cerebral infarcts, particularly small lesions, compared with computed tomography (CT) due to stronger field magnets, thinner slices, and different pulse sequences.³² DW-MRI has an average sensitivity of 94% and specificity of 97% in detecting stroke in humans.³³ It has been used extensively as a surrogate for cerebral embolization after catheter-based and surgical cardiovascular interventions.^{31, 34} In addition, standardized endpoint definitions for TAVI trials (VARC-2) include MRI or computed tomographic neuroimaging as an important supplement to the clinical diagnosis of stroke and TIA, as well as a requisite for diagnosing stroke in patients with non-focal global encephalopathy.³⁵

Several small studies (Tables 1-4) have reported DW-MRI data after unprotected TAVI. Foci of restricted cerebral perfusion on DW-MRI (cerebral ischemic lesions) are present in approximately 77% of patients (reported range 58% to 93%) after TAVI (Table 1). Most patients have multiple lesions (mean 4.6) (Table 2), distributed bilaterally in a pattern suggesting cerebral embolization. Several studies have reported the volume of single (Table 3) and total per-patient (Tables 4 and 5) lesion volumes after TAVI, with wide variance between studies; the relative degree to which this variation is attributable to methodological and patient-level differences in the extent of affected cerebral tissue is unclear.

Table 1. Reported Incidence of Ischemic Lesions on Post-TAVI DW-MRI

Study	Sample Size (N)	Subjects with Lesions (n)	Proportion with Lesions (n/N)
Arnold 2010³⁶	25	17	68%
Astarci 2013^{37†*}	44	41	93%
Fairbairn 2012³⁸	31	24	77%
Ghanem 2013^{39†}	39	28	72%
Kahlert 2010^{40 *}	32	27	84%
Knipp 2013⁴¹	12	7	58%

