5.4.2.1.3 Secondary Efficacy Endpoints

5.4.2.1.4 Phase I: Hierarchical composite efficacy endpoint, determined by pair-wise comparisons among all subjects according to the following pre-specified hierarchy of adverse outcomes:

- All-cause mortality or any stroke (disabling or non-disabling) [evaluated at 30 days]
- NIHSS worsening (increase from baseline) [evaluated at 2-5 days post-procedure] or Montreal Cognitive Assessment worsening (decrease of 3 or more points from baseline) [evaluated at 30 days]
- Total volume of cerebral ischemic lesions detected by diffusion-weighted magnetic resonance imaging (DW-MRI) 2 to 5 days post-procedure

Each subject in the intervention group will be compared with each and every subject from the control group based on the above hierarchy according to the Finkelstein-Schoenfeld method.² For example, if Subject A dies or has stroke and Subject B survives free of stroke to 30 days, Subject B wins (score +1) and Subject A loses (score -1). If both subjects die or have a stroke, it is equilibrium (score 0). If both subjects survive free of stroke to 30 days, the comparison moves to the next tier of the hierarchy.

After all between-subject comparisons have been performed, scores are summed to obtain a cumulative score for each subject, and outcomes between treatment groups are then compared.

5.4.2.1.5 Imaging Efficacy Endpoints (Phase I and Phase II):

- Presence of cerebral ischemic lesions detected by DW-MRI, evaluated 2 to 5 days post-procedure
- Number of cerebral ischemic lesions detected by DW-MRI, evaluated 2 to 5 days post-procedure
- Per-patient average single cerebral ischemic lesion volume detected by DW-MRI, evaluated 2 to 5 days post-procedure
- Single cerebral ischemic lesion volume (lesion-level analysis) detected by DW-MRI, evaluated at 2 to 5 days post-procedure
- Total volume of cerebral ischemic lesions detected by DW-MRI, evaluated 2 to 5 days post-procedure

5.4.2.1.6 Neurologic Efficacy Endpoints (Phase I and Phase II):

- NIHSS worsening, defined as an NIHSS score increase from baseline [baseline score compared with score evaluated at 2-5 days post-procedure and at 30 days]
- New neurologic impairment, defined as an NIHSS score increase from baseline accompanied by the presence of cerebral ischemic lesions [evaluated at 2-5 days post-procedure and at 30 days]

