12.2.4.1.2 Primary Efficacy Endpoint

Sample size for assessing superiority of Intervention over Control with respect to the hierarchical composite primary efficacy endpoint was estimated using the following assumptions:

- All-cause mortality or any stroke at 30 days will occur in ~11% of Control subjects and ~6% of Intervention subjects (5% absolute reduction, ~45% relative reduction)
- Among subjects without all-cause mortality or any stroke to 30 days, NIHSS worsening 2-5 days post-procedure will occur in 9% of Control subjects and 6% of Intervention subjects (3% absolute reduction, 33.3% relative reduction)
- Among subjects without all-cause mortality or any stroke to 30 days and without NIHSS worsening 2-5 days post-procedure, MRI findings will occur in 89% of Control subjects and in 73% of intervention subjects (16% absolute reduction, 17.9% relative reduction).
- Among subjects without all-cause mortality or any stroke to 30 days, without NIHSS worsening 2-5 days post procedure, but with MRI findings, lesion volumes can be divided into 3 out of 4 subsets- 0 mm³, >0-50 mm³, >50-150 mm³ and >150 mm³. For these volume subsets, we expect rates of 11%, 7%, 33% and 48%, respectively, in the control group and 27%, 19%, 7.5%, and 46%, respectively, in the intervention group.
- For sample size calculations a relative reduction of 30% is expected in each lesion volume subset, based on the comparison of total lesion volumes between device and control groups in DEFLECT I, MISTRAL C⁷³ SENTINEL⁹ and CLEAN-TAVI⁷⁴.
- The smallest detectable difference in MRI is a single voxel. In addition, inter-rater mean differences between two independent observers was 15% or ~5 voxels (40.5 mm³) in the KSH Methodology/Reproducibility Study (data on file). Accordingly, a meaningful difference to declare a win/lose between MRI lesion volumes was set at a 15% relative difference or a 50 mm³ absolute difference.

- Loss to post-procedure DW-MRI follow-up is expected to occur in 15% of all subjects (due to contraindications to post-procedure DW-MRI [e.g., pacemaker implantation] or subject non-compliance)
- Loss to follow-up for all other reasons is expected to be 5%.
- Overall α (one-sided)=0.025; (see §12.4.2)

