To determine the required sample size, calculations were performed by simulating 5000 samples on SAS software postulating the above parameters; mortality and stroke rates and proportions of patients with NIHSS worsening, any MRI lesions and volumes divided to subsets were simulated by a random binary function.

An evaluable sample size of 225 subjects (2:1 randomization with 150 in the Intervention group and 75 new Control subjects) is sufficient to demonstrate superiority of the Intervention group to the Control group for the primary efficacy endpoint when pair-wise comparisons are made between subjects using the Finkelstein-Schoenfeld method,² and outcomes between treatment groups are compared by the chi-square test.

Therefore, the initial randomized cohort sample size of 225 subjects (150 in the Intervention group and 75 new control subjects) will have >80% power to demonstrate superiority of the Intervention group for the primary efficacy endpoint (one sided $\alpha=0.025$). Notably, in several simulations, considering different distributions for lesion volume and different distributions for death/ stroke, the study power remained greater than 80%.

Adding the 63 control subjects already enrolled in REFLECT Phase I for a total of 138 control subjects would increase the power to at least 92% to demonstrate superiority of the primary efficacy endpoint. 5% loss to follow up is included.

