12.4.5.1.2 Secondary Efficacy Endpoints

- **Imaging Efficacy Endpoints**

All secondary imaging efficacy endpoints will be reported by treatment group in the eITT Population of subjects with available data using descriptive statistics. No formal hypothesis testing will be performed, and there is no plan to adjust alpha to account for multiple testing of exploratory secondary endpoints. Statistics for continuous variables will include mean, median, standard deviation, minimum, maximum, and sample size for each treatment group. Binary variables will be summarized using frequencies, percentages, and sample size for each treatment group.

The eITT analysis will be considered primary. As a secondary analysis, all secondary imaging efficacy endpoints will be evaluated in the ITT population of evaluable subjects. An additional analysis will also be performed in the PT population.

An additional analysis of secondary imaging efficacy endpoints with adjustment for pre-existing cerebral lesion volume will also be performed in the primary eITT analysis population. These endpoints include presence of cerebral ischemic lesions (§□), number of cerebral ischemic lesions (§□), per-patient average single cerebral ischemic lesion volume (§□), single cerebral ischemic lesion volume (§□), and total volume of cerebral ischemic lesions (§□), which vary by their distribution from binary (as in "presence of cerebral ischemic lesions") to Poisson, or possibly negative binomial in others. The choice of a specific model used for adjustment will therefore depend on the actual distribution of the dependent variable (logistic, log-linear, Poisson, negative binomial or quantile). The models will include the study group and pre-existing cerebral lesion volume as independent variables.

- **Neurologic Efficacy Endpoints**

All secondary neurologic efficacy endpoints will be reported by treatment group in the eITT Population of evaluable subjects (Roll-In subjects are excluded) using descriptive statistics. No formal hypothesis testing will be performed, and there is no plan to adjust alpha to account for multiple testing of exploratory secondary endpoints. Statistics for continuous variables will include mean, median, quartiles, standard deviation, minimum, maximum, and sample size for each treatment group. Binary variables will be summarized using frequencies, percentages, and sample size for each treatment group.

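### The adjusted model for the lesion-level volume endpoint makes no provision for several lesions coming from one randomised patient

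*Combined protocol and SAP*

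**What the plan says.** Section 5.4.2.1.5 lists, separately from the per-patient average, the endpoint "Single cerebral ischemic lesion volume (lesion-level analysis) detected by DW-MRI, evaluated at 2 to 5 days post-procedure". The unit of analysis is therefore the lesion.

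Section 12.4.5.1.2 reports the imaging endpoints descriptively in the eITT population, without formal testing. It then adds an analysis adjusted for pre-existing cerebral lesion volume and names all five imaging endpoints for it, including the lesion-level one. On the form of the model it says "The choice of a specific model used for adjustment will therefore depend on the actual distribution of the dependent variable", and the candidates are "logistic, log-linear, Poisson, negative binomial or quantile". On the terms it says "The models will include the study group and pre-existing cerebral lesion volume as independent variables". Both terms take one value per patient.

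No section supplied describes a subject effect, a GEE, a cluster-robust variance or any other way of handling several lesions from the same patient.

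**The concern.** Patients are randomised, not lesions, so study group is constant within a brain. A one-level model fitted to lesions takes its precision from the number of lesions. If lesions in one patient resemble each other, the information about the device effect is closer to the number of patients, and the model-based standard error is too small. The specification suits presence, count, per-patient average and total volume, which have one row per patient. It does not carry over to the lesion-level endpoint.

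At stake is the stated precision of one adjusted device-effect estimate. A few patients with many lesions could make that estimate look more certain than the number of randomised patients supports.

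**Working it through.** **Reproducing the plan's figure.** The average row of Table 2 gives 4.6 lesions per patient. The simple mean of the seven study means is (7.9 + 4.2 + 3.4 + 3.6 + 1.8 + 7.2 + 4.2)/7 = 32.3/7 = 4.61, which agrees.

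**Patients and lesions.** Section 12.2.4.1.2 plans "2:1 randomization with 150 in the Intervention group and 75 new Control subjects" and states "Loss to post-procedure DW-MRI follow-up is expected to occur in 15% of all subjects". That leaves 150 × 0.85 ≈ 128 and 75 × 0.85 ≈ 64 patients with MRI, 192 in all. At 4.6 lesions each, the model would have about 192 × 4.6 ≈ 883 rows.

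**Formulas.** With unequal lesion counts the effective cluster size is m_w = mean + SD²/mean. Patients without lesions do not alter it. The design effect is DEFF = 1 + (m_w − 1) × ICC. A nominal 95% interval that ignores clustering then covers 2Φ(1.96/√DEFF) − 1.

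**Cluster size.** If every patient had 4.6 lesions, m_w = 4.6. With the spread in Table 6 for protected TAVI (mean 5.1, SD 6.1), m_w = 5.1 + 37.21/5.1 = 12.4.

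**Assumption.** The documents give no ICC, so a range is shown.

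| Assumed ICC | DEFF, equal counts | Coverage | DEFF, Table 6 spread | Coverage |
|---|---|---|---|---|
| 0 | 1.00 | 95.0% | 1.00 | 95.0% |
| 0.05 | 1.18 | 92.9% | 1.57 | 88.2% |
| 0.10 | 1.36 | 90.7% | 2.14 | 82.0% |
| 0.20 | 1.72 | 86.5% | 3.28 | 72.1% |
| 0.30 | 2.08 | 82.6% | 4.42 | 64.9% |

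The three studies in Table 2 that report an SD give these results at ICC 0.05 and 0.30:

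- mean 4.2, SD 6.5 (m_w 14.26): 87.1% and 62.0%
- mean 3.4, SD 5.1 (m_w 11.05): 89.0% and 67.2%
- mean 1.8, SD 1.9 (m_w 3.81): 93.4% and 85.1%

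**Simulation check.** There were 3,000 runs per ICC with 128 and 64 patients. Lesion counts were negative binomial with mean 4.6 and SD 6. Log volume was regressed on group and one patient-level covariate, with no device effect.

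| Assumed ICC | Coverage, no clustering | Coverage, clustered by subject | Mean clustered SE ÷ mean unclustered SE |
|---|---|---|---|
| 0 | 95.0% | 94.3% | 0.97 |
| 0.05 | 88.0% | 93.5% | 1.20 |
| 0.10 | 83.2% | 94.0% | 1.39 |
| 0.20 | 72.0% | 93.5% | 1.70 |
| 0.30 | 65.4% | 92.9% | 1.97 |

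The simulation agrees with the formula. Clustering by subject brings coverage back to about 93% to 94%.

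**The case against.** The strongest reply is that the plan promises no output that would be wrong. The main report is descriptive, no test is planned, no interval is named for this endpoint, and the model is an additional analysis. That stands, and it sets the priority. It does not remove the point: a regression with study group as a term exists to estimate a device effect, and any interval or p-value taken from it inherits the understated standard error.

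A second reply is that the plan says what the models will include and does not rule out anything further. A reader might infer that it expressly assumes independent lesions. It does not; it is silent on variance, and a robust variance could be added to several of the listed model families. Section 12.1 also defers further clarification to the SAP. That deferral is general, however, and nothing supplied tells a programmer to do other than fit lesions as separate rows.

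A third concerns evidence for the ICC. A reader might infer strong within-patient similarity from the 22-patient study in Tables 2 to 4: one subject had a total of 70.3 cm³ and no subject had more than 19 lesions, so that brain averaged at least 70.3/19 = 3.7 cm³ per lesion, against a study mean of 0.76. The documents do not support so general a conclusion. The study's total is 22 × 4.3 = 94.6 cm³, so this one subject holds 70.3/94.6 = 74% of it. Removing the subject gives (94.6 − 70.3)/21 = 1.16, the mean in Table 5, whose footnote attributes the exclusion to a major stroke. The SD of total volume then falls from 14.9 to 2.08. The tables also do not reconcile per lesion: 94.6/(22 × 3.4) = 1.26 cm³, not 0.76. They cannot supply an ICC.

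Finally, a reader might infer that a main efficacy claim is exposed, because lesion volume is prominent in the trial. The volume in Tier 4 and in the fifth hypothesis-driven secondary endpoint is the total per patient, which is one value per subject. The plan also keeps a patient-level counterpart, the per-patient average lesion volume.

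**Conclusion.** The point holds as a minor one. The stated specification does not fit the one imaging endpoint whose unit is the lesion, and following it understates the device-effect standard error whenever the within-patient correlation is positive.

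The size depends on an ICC that the documents do not give. For 0.05 to 0.30, coverage of a nominal 95% interval is about 88% to 65% with the Table 6 spread of counts. It is 93% to 83% if every patient had 4.6 lesions, and there is no error at ICC 0. These figures also assume a linear model on the log scale, standing in for whichever listed family is chosen.

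The consequence is confined to this additional adjusted analysis. The primary endpoint, the alpha-controlled secondary endpoints and the other four imaging endpoints do not change.

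**What to change.** In section 12.4.5.1.2, take the lesion-level endpoint out of the shared model sentence and give it its own. For example: *Single lesion volume (lesion level) will be modelled on the log or cube-root scale with study group and pre-existing lesion volume as fixed effects and subject as the cluster, using GEE with robust variance or a random subject intercept; if a quantile model is used, intervals will come from a bootstrap that resamples subjects.* Section 12.4.3 already uses the cube root for total lesion volume. Choose one method in advance, because GEE and a random intercept can weight patients with many lesions differently.

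In the descriptive table, show the number of subjects beside the number of lesions, since the planned sample size does not say which is meant.

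The cost is a sentence of text and one statement in the analysis code, with no new data or patients. The only downside is a wider interval for this endpoint if lesions within patients are correlated.

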12.4.5.1.3 Secondary Performance Endpoints

All secondary performance endpoints will be reported by treatment group in the ITT population of evaluable subjects (RI subjects are excluded) using appropriate descriptive statistics (sample size, mean, standard deviation, median, minimum, maximum for continuous characteristics; counts and percentages of patients for dichotomous characteristics). No formal hypothesis testing will be performed, and there is no plan to adjust alpha to account for multiple testing of exploratory secondary endpoints.

The ITT analysis will be considered primary. As a secondary analysis, all secondary safety and performance endpoints will be evaluated in the AT population of evaluable subjects.

12.4.6 Other Measures

Other Measures will be reported by treatment group in the ITT population of evaluable subjects (RI subjects are excluded) using descriptive statistics. No formal hypothesis testing will be performed.

The ITT analysis will be considered primary. As a secondary analysis, Other Measures will be evaluated in the AT population of evaluable subjects. An additional analysis will also be performed in the PT population.

12.4.7 Subgroup Analyses

Subgroup analyses will be performed for all primary and secondary endpoints in their respective primary analysis populations for the following subgroups, and results will be reported by treatment group using descriptive statistics:

- Subjects with paroxysmal or persistent atrial fibrillation (AF) at baseline
- Subjects by valve prosthesis type (Edwards vs. Medtronic)

12.4.8 Roll-In Population Analysis

The Phase II Roll-In population will be pooled with the Phase II intervention group for the primary analysis of the primary safety endpoint. The Roll-In patient population will also be

used for a separate analysis of all primary and secondary endpoints and other measures. Additional analyses will evaluate primary and secondary endpoints in the pooled population of Roll-In Subjects plus Evaluable Subjects. The results of all analyses will be reported using descriptive statistics.

12.4.9 Additional Analyses

The following data will be summarized using descriptive statistics presented by treatment group:

- Subject enrollment and data compliance by site and visit (data compliance at each visit is percent of patients whose data forms have been collected and entered divided by the percent of patients whose forms should have been collected and entered) (ITT, eITT, PT, and AT populations)
- Frequency (number and percent of patients) with each type of concomitant medication (AT population)
- Frequency (number and percent of patients) with each site-reported Treatment Emergent AE overall and by MedDRA system organ class and preferred term (a treatment emergent AE is an AE that started or worsened during or after the index procedure) (AT population)
- Frequency (number and percent of patients) with each site-reported Treatment Emergent Serious AE overall and by MedDRA system organ class and preferred term (AT population)
- Frequency (number and percent of patients) with each site-reported Treatment Emergent AE or SAE, by CEC-adjudicated relationship to the investigational device or procedure (AT population)
- Protocol deviations (number and percentage of patients with each deviation type) (ITT population)
- Kaplan-Meier plots for MACCE and TAVI early safety through 30 days (AT Population; patients without an event will be censored at 30 days or day of withdrawal, whichever is earlier)
- Detailed listings on primary and secondary endpoints, site-reported AE as well as protocol deviations

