9.7 End-points Potentially Meeting End-point Criteria

Investigators are instructed to report all cardiovascular events and all adverse events potentially meeting end-point criteria. These events will be documented in the case report form as SAEs and be assessed by the medical monitor. Events classified as potential end-points will then be sent to CEC adjudication (§11.2).

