9.8.2 Relatedness

The investigator will use the following definitions to assess the relationship to the device:

Not related	The cause of the AE is known and the event is not related to any aspect of study participation.
Unlikely to be related	There is little or no temporal relationship to the study device and/or a more likely alternative etiology exists.
Possibly related	There is a reasonable possibility that the event may have been caused by study participation. The AE has a timely relationship to the study procedure(s); however, follows no known pattern of response , and an alternative cause seems more likely or there is significant uncertainty about the cause of the event.
Probably related	It is likely that the event was caused by study participation. The AE has a timely relationship to the study procedure(s) and follows a known pattern of response ; a potential alternative cause, however, may explain the event.
Related	A related event has a strong temporal relationship and an alternative cause is unlikely.

If the relationship between any adverse event and the use of the investigational medical device is considered to be possibly or probably related, that event will be classified as an ADE or SADE.

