9.10 Expected Adverse Events

As with any endovascular intervention, TAVI involves some risks and possible complications. The following anticipated events have been identified as possible complications of TAVI procedures:

- Acute cardiovascular surgery (need for)
- Acute coronary artery occlusion
- Acute myocardial infarction
- Acute neurological events such as stroke, transient ischemic attack (TIA), and encephalopathy
- Allergic reaction to contrast, antiplatelet therapy or device component materials
- Angina pectoris
- Anesthesia reactions
- Aneurysm or pseudoaneurysm
- Arteriovenous fistula
- Ascending or descending aorta trauma
- Atrial or ventricular arrhythmias or fibrillation or sustained heart palpitations requiring therapy
- Bleeding complications such as hematoma and hemorrhage
- Blood loss requiring transfusion
- Bowel ischemia
- Coronary artery or other vascular injury, dissection, or perforation (which may require repair)
- Embolism (air, tissue, device, or thrombus)
- Fever
- Femoral nerve damage
- Hemodynamic changes
- Hypertension or hypotension (sustained requiring therapy)
- Infection, including endocarditis and septicemia
- Pain (at the femoral puncture site, abdominal, back, or other)
- Percutaneous coronary intervention (need for)
- Peripheral ischemia, peripheral nerve damage

- Pulmonary edema
- Pyrogenic reaction
- Renal complications, injury, or failure
- Unstable angina
- Vascular complications which may require vessel repair
- Vessel spasm (sustained, not responding to therapy)

In addition to the risks listed above, the potential risks specifically associated with the TriGuard HDH or TriGUARD 3 procedure include, but may not be limited to, the following:

- Dissection of the innominate artery by improper manipulations, disruption or migration of the TriGuard HDH CEPD filter due to passage of other instrumentation, e.g.: balloon, stent, catheter, wire
- Blue toe syndrome or blue discoloration of a toe
- Femoral bleeding at the access site
- Local trauma to the aortic wall due to device migration

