11.2 Clinical Events Committee (CEC)

The CEC will be responsible for adjudicating all site-reported cardiovascular events and all adverse events potentially meeting endpoint criteria, in an ongoing fashion during the trial. In order to fully capture all endpoints, events potentially meeting end-point criteria will be considered an SAE (even if they do not result in death or prolong the hospitalization) and sent to the medical monitor for further assessment. Events appropriately classified as potential endpoints by the medical monitor will be sent to CEC for adjudication.

Events potentially meeting end-point criteria and therefore defined as SAE for this purpose include:

- Death
- Stroke/TIA or any other Neurological Dysfunction (NeuroARC definitions)
- MI or Coronary artery obstruction requiring intervention
- Bleeding (including life-threatening or disabling bleeding, Major and Minor bleeding)
- Acute kidney injury (stage 2 or 3 or requiring dialysis)
- Major vascular complications
- Valve-related dysfunction requiring repeat procedure

The CEC will include at least one interventional cardiologist with relevant clinical experience and one neurologist with experience in clinical trials involving stroke who are otherwise independent of the Sponsor or the conduct of the study. Members will not have scientific, financial or other conflicts of interest related to Keystone Heart Ltd. or the Investigators. The CEC will operate and conduct all meetings and event reviews independent of the Sponsor unless specific expert knowledge regarding the characteristics or function of the study device is requested by the CEC from the Sponsor.

The CEC will meet regularly throughout the study to adjudicate events in an ongoing and timely fashion. The adjudication process, event definitions and required source document materials for each type of event will be pre-specified in the CEC Charter prior to the onset of the trial. The adjudication process will include CEC member review of copies of all relevant medical records and imaging studies associated with an event reporting. All adjudication decisions will be made by the CEC in an independent fashion based upon review of all available medical evidence associated with an event.

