- Access site or access-related vascular injury (dissection, stenosis, perforation, rupture, arterio-venous fistula, pseudoaneurysms, hematomas, percutaneous closure device failure) **not leading to** death, life-threatening or major bleeding, visceral ischemia or neurological impairment OR
- Distal embolization treated with embolectomy and/or thrombectomy and not resulting in amputation or irreversible end-organ damage OR
- Any unplanned endovascular stenting or unplanned surgical intervention not meeting the criteria for a major vascular complication OR
- Vascular repair or the need for vascular repair (via surgery, ultrasound-guided compression, transcatheter embolization, or stent-graft)

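### The only adverse-event table by device relationship relies on CEC adjudication that not every event receives, and the ADE/SADE rule in 9.8.2 omits the strongest relatedness grade

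*Combined protocol and SAP*

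**What the plan says.** **The table.** Section 12.4.9 lists, for the As Treated population, the frequency of patients "with each site-reported Treatment Emergent AE or SAE, by CEC-adjudicated relationship to the investigational device or procedure". It also plans treatment-emergent AE and serious AE tables by MedDRA class and term, without relationship, and "Detailed listings on primary and secondary endpoints, site-reported AE as well as protocol deviations".

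**Which events the CEC sees.** Section 11.2 opens with a wide remit: "The CEC will be responsible for adjudicating all site-reported cardiovascular events and all adverse events potentially meeting endpoint criteria". The Study Committees entry in the synopsis gives the same remit and adds that relationship is adjudicated in the Intervention and Roll-In groups. Later in 11.2 the route is narrower: "Events appropriately classified as potential endpoints by the medical monitor will be sent to CEC for adjudication". Section 9.7 agrees with the narrower route: "Events classified as potential end-points will then be sent to CEC adjudication".

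**Investigator relatedness.** Section 9.8 has relatedness recorded for all AEs, and 9.8.2 supplies a five-grade scale: not related, unlikely, possibly, probably, related. The closing rule in 9.8.2 is that an event whose relationship to device use "is considered to be possibly or probably related, that event will be classified as an ADE or SADE". Section 9.3 defines an ADE as any AE related to use of the device, and 9.4 builds the SADE on it.

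**Device-specific risks.** Section 9.10 names four, among them "Blue toe syndrome or blue discoloration of a toe".

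**The concern.** The table's rows are all site-reported AEs and SAEs, but its classifying variable exists only for events that went through the CEC. Rows outside CEC review have no value, and the plan does not say how they will be shown. No other planned table supplies one: the secondary safety endpoints are also reported by relationship (12.4.5.1.1), but that too is CEC-determined and confined to endpoints. No count of ADEs or SADEs is planned.

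This matters because of how the device works. It diverts debris to the descending aorta, and 12.3.3 describes its access through the contralateral femoral artery. Limb embolic events and access-site injuries are therefore among the harms a reader of the safety report will look for by attribution, and the milder ones are the least certain to reach the CEC.

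The 9.8.2 wording matters for a different reason. SADE status carries its own reporting line in 9.9.2 and Table 13, so the sentence that assigns the class should agree with the definition of the class.

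**Working it through.** No arithmetic underlies this part of the plan and there is no figure to reproduce. The check sets the passages side by side.

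**Step 1: remit against routing.** The synopsis and the first sentence of 11.2 give the CEC all cardiovascular events plus potential endpoint events. Section 9.7 and the later sentence of 11.2 send it only what the medical monitor classes as a potential endpoint. The two differ for cardiovascular events that are not endpoints. The list in 11.2 includes bleeding of every grade but, for vascular events, only major complications. Its neurological entry is limited to NeuroARC definitions, and the category in Appendix I without CNS injury covers TIA and delirium, not peripheral nerve injury.

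**Step 2: what reaches the CEC under each reading**, using the Appendix I definitions.

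| Event | Wide remit | Narrow routing |
|---|---|---|
| Allergy to a device material, not an endpoint event | No | No |
| Transient access-site nerve injury | No | No |
| Minor vascular complication without bleeding, including treated distal embolization | Yes, if counted as cardiovascular | No |
| Blue toe short of the major criteria | Yes, if counted as cardiovascular | No |
| Blue toe meeting a major criterion (new ipsilateral limb ischemia; distal embolization needing surgery or causing amputation or irreversible organ damage) | Yes | Yes |
| Permanent access-site nerve injury, or nerve injury needing surgery | Yes | Yes |
| Femoral access-site bleeding, any grade | Yes | Yes |

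The third row rests on Appendix I, which classes as minor "Distal embolization treated with embolectomy and/or thrombectomy and not resulting in amputation or irreversible end-organ damage". Minor vascular complications are in no endpoint and not on the 11.2 list.

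The first two rows have no relationship value under either reading. The next two depend on which sentence the medical monitor follows.

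**Step 3: the four device-specific risks in 9.10.** Femoral bleeding reaches the CEC at any grade. Innominate dissection and aortic-wall trauma fall within the cardiovascular remit and, depending on severity, may be major vascular complications. Blue toe syndrome reaches the CEC if it meets a major criterion or is handled as a cardiovascular event. Only the milder case, under the narrow routing, does not.

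**Step 4: the ADE/SADE rule.** Three of the five grades are at or above *possibly*: *possibly*, *probably* and *Related*. The rule names two, so 3 − 2 = 1 is left out, and it is the strongest. Under 9.3, an event graded *Related* is an ADE by definition. The two passages do not agree.

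**The case against.** Much can be said for the plan, and several stronger readings fail.

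- **A reader might infer that blue toe syndrome, or access-site harm in general, never reaches the CEC.** The documents do not support this. New ipsilateral limb ischemia, severe distal embolization and permanent nerve injury are major vascular complications, bleeding of every grade is on the CEC list, and the stated remit covers all cardiovascular events. Major vascular complications related to the device are themselves a secondary safety endpoint.
- **A reader might infer that these events go unreported.** They do not. All site-reported treatment-emergent AEs and SAEs are tabulated by MedDRA class and term and by treatment group, and AEs are listed. A marked excess over control could be seen there without any attribution. UADEs have a separate definition (9.5) and reporting route (9.9.3).
- **A reader might infer that events graded *Related* lose ADE status, or that a planned device-effect rate is understated because of 9.8.2.** Section 9.3 already covers these events, and 12.4.9 plans no ADE or SADE rate that the sentence could distort. It is a drafting inconsistency.
- **Further detail may sit elsewhere.** Section 12.1 defers clarifications on endpoint assessment to the SAP, and 11.2 defers the adjudication process to the CEC Charter. Neither is among the text reviewed as a separate document.

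These points narrow the issue but do not remove it. Even the widest remit excludes non-cardiovascular, non-endpoint events from the variable that the table uses. Comparison by MedDRA term is not attribution, and 12.4.9 does not say that the listings will show relatedness.

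**Conclusion.** The point holds in limited form. The one planned AE frequency table by device relationship uses a variable that some of its rows will not have. Under any reading this affects non-cardiovascular, non-endpoint events. Under the narrow routing it also affects minor vascular complications without bleeding and blue toe events short of the major criteria. The loss is of tabulated attribution, not of the events themselves. Separately, the 9.8.2 classification sentence omits *Related* and is inconsistent with 9.3.

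The documents give no rates for the affected event types, so the number cannot be computed, and no claim that many events are involved can be sustained. No primary endpoint, hypothesis test or success criterion is touched. The conclusion assumes that neither a separate SAP nor the CEC Charter widens adjudication to all AEs or adds a table by investigator relatedness. It is worth correcting because the needed field is already collected for every AE.

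**What to change.** 1. In 12.4.9, tabulate AEs and SAEs in device-exposed subjects by CEC-adjudicated relationship where it exists and by investigator-assessed relatedness otherwise, with the source shown for each. The source matters because the CEC judges relationship to device or procedure, while the 9.8.2 scale is introduced as relationship to the device.
2. Reconcile the CEC remit in the synopsis and the first sentence of 11.2 with the routing in 9.7 and later in 11.2, so that it is clear whether non-endpoint cardiovascular events are adjudicated.
3. Reconcile the classification sentence in 9.8.2 with the definition in 9.3, so that the *Related* grade is not left out.

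The cost is one extra table from data already on the AE form and wording changes in a few sections. The downside is that the reported device-related event rate may be slightly higher.
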